9.1 Study Monitoring Plan	29
9.2 Auditing and Inspecting	30
10 Ethical Considerations	30
10.1 Risks	30
10.2 Benefits	31
10.3 Risk Benefit Assessment	31
10.4 Informed Consent Process / HIPAA Authorization	31
11 Study Finances	32
11.1 Funding Source	32
11.2 Conflict of Interest	32
11.3 SUBJECT STIPENDS OR PAYMENTS	32
12 Publication Plan	33
13 References	34

Study Summary

Title	Remote Geo Smoking Study: Behavioral and Geospatial Correlates of Smokers' Exposure to Retail Environments
Short Title	Remote Geo
IRB Number	850796
Methodology	This study will utilize a randomized trial to examine the effects of point-of-sale tobacco marketing on smoking behaviors and brain activity. After a two week observational period, participants will be randomized to one of three behavioral intervention conditions for the duration of a four week intervention period.
Study Duration	Five years
Study Center(s)	Single-center
Objectives	
 The primary objectives of this study are to understand the effects of point-of-sale tobacco marketing (POST-M) on smoking behavior and cravings in smokers. We will examine whether experimental group assignment affects cigarette cravings and cigarette consumption during the intervention period relative to the baseline period. For a subset of participants, we will examine brain responses during the smoking cue reactivity task.
Number of Subjects	343 [Actual]
Main Inclusion and Exclusion Criteria	
Key Inclusion Criteria for remote participation:
 
 Be between the ages of 21-65 Smoke at least 5 cigarettes a day for the past 6 months Own an iPhone or Android smartphone that can be used on a daily basis Be residents of Pennsylvania, New Jersey, or Delaware Read and speak English fluently Fully vaccinated against COVID-19 
Key Exclusion Criteria for remote participation:
 
 Current enrollment or plans to enroll in a smoking cessation program in the next 3 months Plan to use nicotine substitutes or smoking cessation treatments in the next 3 months Urine cotinine concentration below 200ng/mL Pregnancy Inability or refusal to complete study tasks 
The complete list of study inclusion and exclusion criteria, including exclusion criteria for the fMRI subset, is included within the Characteristics of the Study Population section of this protocol.

Intervention	Random assignment of retail environment (high POSTM; low POSTM, control [no store]) to visit 5 times per week during the 4-week intervention period.
Statistical Methodology	We will use linear regression and multilevel models (in R) to test our hypotheses, as well as tools from nipype, SPM, and fmriprep to process and model fMRI data.
Data and Safety Monitoring Plan	The principal investigator will monitor the safety, privacy, and data integrity during the course of the study. In addition, we will provide the required project reports to the sponsor.

- **Background and Study Rationale**

This document is a protocol for a human research study. This study will be conducted in full accordance with all applicable University of Pennsylvania Research Policies and Procedures and all applicable Federal and state laws and regulations.

1 Introduction

Cigarette smoking is the leading cause of preventable death and illness in the United States and throughout the developed world. Recent work suggests detrimental links between exposure to point-of-sale tobacco marketing (POSTM), increases in cigarette cravings, and the failure to quit smoking. Understanding how individuals are influenced by and react to environmental cues when making health decisions is critical to cancer control efforts and policymaking. We propose to use an innovative set of methods to test whether repeated, real-world exposure to POSTM affects smoking behavior, and whether this is mediated by changes in craving and neural responses to POSTM. Our approach combines mobile-phone based geolocation tracking, ecological momentary assessment (EMA), and functional magnetic resonance imaging (fMRI). Research using geospatial location tracking and surveys suggests that high levels of POSTM exposure may increase craving; however, correlational studies preclude causal inferences about POSTM effects. Relatedly, laboratory studies have documented neural and behavioral reactivity to standardized visual smoking cues, such as photographs of cigarettes in an ashtray, but the brain's response to naturalistic POSTM exposure has not been explored. By adding the ecological validity of observational field methods to the mechanistic insight of neuroimaging, and causal inferences from an experimental pre-post design, we aim to significantly advance actionable insight about POSTM effects in cancer control.

1.1 Background and Relevant Literature

Summary:

The tobacco industry has come to rely increasingly on point-of-sale tobacco marketing (POST-M), with large displays near cash registers in retail outlets such as convenience stores and gas stations [1]. Recent work utilizing geospatial location tracking has found that smoking

lapses while smokers are trying to quit are more likely on days when smokers are exposed to POST-M, particularly when their general tobacco craving levels are otherwise low [2]. This suggests that POST-M exposure may increase craving, making abstinence more difficult. This finding converges with recent survey results demonstrating that during quit attempts, a significant percentage of smokers experience urges to purchase cigarettes when exposed to POST-M, and feel that the removal of POST-M would make quitting easier [3]. These reports indicating that incidental exposure to cigarette cues adversely affects smoking abstinence are supported by laboratory studies. A typical laboratory cue reactivity paradigm involves presenting participants with pictures or video of smoking cues, such as a hand holding a cigarette, followed by a measurement of participants' craving intensity. Smoking abstinence has been found to potentiate self-reported craving in response to cigarette cues [4-7,8], suggesting a mechanism for the finding that exposure to POST-M during a quit attempt leads to poorer outcomes. No studies, however, have experimentally manipulated exposure to POST-M cues *in vivo*. To this end, we will examine whether assigning smokers to a high or low level of POST-M exposure as part of their daily routine affects several smoking outcomes. A location tracking smartphone application (Google Maps) will be used to document participants' exposure to retail outlets and link each person to the retail environment. Measurements will assess longitudinal tobacco-use patterns and perceptions across the study period, as well as changes in cravings. If it is the case that low POST-M exposure reduces smoking, this emphasizes the importance of further regulation of retail advertising for tobacco.

In addition to the hypotheses and analysis plans described here, the study team has preregistered additional hypotheses and analysis plans which are not the focus of the clinical trial component of the study. These are available at <https://osf.io/kyb64/registrations>.

Background:

Tobacco dependence is a significant public health problem. Cigarette smoking is the leading cause of preventable death and illness in the United States and throughout the developed world¹. Smoking increases the odds of developing the most frequently diagnosed cancers and other leading causes of death, accounting for 1 in 5 deaths in the US each year^{2,3}. Due to restrictions in other communication outlets, the tobacco industry currently concentrates over 80% of its \$8.1 billion annual marketing budget on retail environments, including **point-of-sale tobacco marketing (POSTM)**⁴⁻⁸. Tobacco advertising and products are placed prominently in "power walls" near or behind cash registers in retail outlets like convenience stores and gas stations^{9,10,11}, such that all customers are exposed to this marketing. This widespread and frequent exposure to POSTM in smokers and nonsmokers alike is of great interest in tobacco control and cancer prevention research worldwide, and has led to recent bans of POSTM in 42% of countries in Europe¹². In this study, we aim to test whether repeated, real-world exposure to POSTM affects smoking behavior through heightened neural smoking cue reactivity and subjective craving. We will test both correlational (Aims 1-2) and causal (Aim 3) pathways. To this end, we propose an innovative combination of geolocation tracking as an ecologically valid, objective measure of real-world POSTM exposure^{13,14}; ecological momentary assessment (EMA)¹⁵ to assess real-time behavior and craving; and functional magnetic resonance imaging (fMRI) to assess neural responses to cigarette cues¹⁶⁻¹⁸. Understanding both the neural (laboratory-based) and behavioral (real-world) consequences of exposure to POSTM will clarify the mechanisms of POSTM impact, and ultimately aid in the design of more effective cancer prevention and tobacco regulatory policies.

How are smokers influenced by point-of-sale tobacco marketing (POSTM)? Past work suggests detrimental relationships between exposure to POSTM and other environmental smoking cues and smoking behavior in individuals (e.g.,^{19,20}) and the larger population (e.g.,²¹)

across countries, measures and study designs (for a review:²²). Within current and recently quit smokers, field work consistently reports associations between POSTM exposure in naturalistic settings, and increased smoking cravings, purchase urges, and impulse purchases^{23–28}. The density of POSTM in an individual's neighborhood, a proxy for exposure, also influences smoking behavior^{29–33}; for example, longitudinal work finds that smokers are more likely to relapse during a quit attempt if they live near a POSTM store³⁴. In a virtual store study, enclosing the POSTM display reduced smokers' purchase attempts and urges to smoke³⁵. This body of research thus suggests that further regulation of POSTM would be beneficial from a cancer control perspective; however, causal evidence linking longitudinal, naturalistic exposure and smoking outcomes, as well as neural evidence supporting the mechanisms of cumulative and causal effects, would substantially bolster science-based policy making.

The significance of geolocation tracking and ecological momentary assessment.

Geolocation tracking provides the unique ability to objectively and unobtrusively assess participants' exposure to POSTM outlets. The recent ubiquity of geolocation tracking built-in to smartphones provides the opportunity for incorporating this methodology into experimental designs with reduced participant burden. This is a significant improvement over prior POSTM exposure work, which is limited by reliance on self-reports of the timing and degree of POSTM exposure, or by the need to initiate or observe single, non-representative exposures. In PA, DE, and NJ, where data collection will take place, obtaining a local cigarette dealer license is mandatory for cigarette retailers³⁶ and listings of licensed outlets are publicly available and updated monthly³⁷. Layering smokers' geolocation tracks onto maps of tobacco retail outlets allows objective quantification of an individual's exposure to POSTM in their natural environment.³⁸ In parallel with geolocation tracking, we will sample participants' behaviors and craving throughout each day using EMA, to capture time-sensitive fluctuations in a representative manner¹⁵. EMA optimally complements the naturalistic geolocation tracking data by tagging participants' location history with reports indicating natural smoking behavior and craving on a moment-to-moment basis. Thus, this project will link individuals' smoking cravings and behavior to the POSTM environment in both time and location. Our team's expertise with mobile device-based EMA collection^{41,42} makes us uniquely suited to conduct this multi-level integrative research.

Combining responses to tobacco-related cues in the real world and cue-reactivity in the neuroimaging laboratory will provide a mechanistic understanding of how POSTM influences smokers. The scientific premise for this study derives from theoretical models and empirical studies of addiction, which suggest that exposure to drug-cues, such as images of drug paraphernalia, enhances craving and consumption behavior in drug users, including smokers^{43,44}. Laboratory work has shown increased neural activity in regions associated with drug cue-reactivity as well as increased ratings of subjective craving in smokers after exposure to smoking cues such as pictures of cigarettes^{16,43}. Craving ratings scale positively with neural cue-reactivity^{17,45,46}, and both metrics predict smoking behaviors in a later ad-lib smoking session^{18,47}. Thus, laboratory experiments implicate neural smoking cue reactivity and cigarette craving as mechanisms linking exposure to smoking cues and behavior. In contrast to many other addictive substances, advertising for cigarettes is professionally produced, legal, and prevalent in smokers' natural environments. Neural cue reactivity effects have been generalized from completely standardized cues to more naturalistic pictures of personal smoking environments, such that exposure to photographs of places where participants often smoke (e.g., one's home) evokes stronger neural and behavioral craving responses than exposure to generic environmental photographs (e.g., an unfamiliar bus stop)^{18,48,49}; however, the generalizability of such effects to POSTM cues and complex retail environments has not been tested. We will test whether baseline exposure to photographs of POSTM elicits activation in the

same brain regions as standardized, proximal smoking cues. A recent meta-analysis shows that a specific set of neural regions consistently responds more strongly to standard smoking cues as compared to neutral images, including the extended visual system, precuneus, posterior cingulate gyrus, anterior cingulate gyrus, dorsal and medial prefrontal cortex, insula, and dorsal striatum¹⁶.

Brain activity as a key, mechanistic indicator of message impact over time. Functional neuroimaging allows an unobtrusive examination of both conscious and unconscious processes induced by exposure to standard smoking cues¹⁶ and mediated messages such as marketing materials⁵⁰⁻⁵². Our team and others have developed multi-method approaches to test the generalizability and predictive validity of laboratory-based neural effects to real-world behaviors⁵¹⁻⁶⁹. This work has shown that neural reactivity to persuasive messaging inside the fMRI scanner reliably predicts health behaviors, including reductions in smoking and sedentary behavior, above and beyond the predictive capacity of commonly used self-reports^{51,59,60,64,65,70-75}. Further, findings obtained in small groups have been shown to be scalable, such that message-induced neural activity in small samples has been used to predict population-level message impact, including the generation of quitline calls⁵¹ and sharing of health-related information^{76,77}. In a past experimental health intervention, our team successfully used brain activity to predict experimental effects on subsequent behavior at timepoints up to a month later⁶².

Causal manipulation of exposure to tobacco marketing. Most extant field work focused on POSTM, despite including large samples and naturalistic settings, has been correlational, with a few notable exceptions. For example, Shadel et al created an experimental convenience store, and found that removal of the POSTM power wall reduced susceptibility to future cigarette smoking in adolescents⁷⁸. The current study proposes to significantly extend these findings by manipulating adult smokers' real-world, daily POSTM exposure over the course of one month, rather than assessing the impact of a single exposure in one experimental session. After an observation period of geolocation tracking and EMA, individuals will be randomly assigned to 1 of 3 groups. Two groups enter and make small, non-tobacco purchases at a store which displays POSTM (tobacco retailer condition) or a store that displays pro-cessation messaging (nontobacco retailer condition). Approaching the register for this purchase constitutes an exposure to POSTM (tobacco retailer condition) or pro-cessation marketing (nontobacco retailer condition). A third group receives no instruction to change their routine exposure to POSTM.

2 Study Objectives

2.1 Primary Objective

The primary objectives are to examine the relationships between smoking behavior, cigarette cravings, and exposure to point-of-sale tobacco marketing. We will examine whether experimental group assignment affects cigarette cravings and cigarette consumption during the intervention period relative to the baseline. For the subset of participants who undergo fMRI scanning, we will compare craving ratings and brain activity during different task conditions.

3 Investigational Plan

3.1 General Design

Study Type: Interventional

Primary Purpose: Other

Study Phase: N/A

Interventional Study Model: Parallel Assignment

Random assignment of retail environment (tobacco retailer, non-tobacco retailer, no store) to visit 5 times per week during the 4-week intervention period

Number of Arms: 3

Masking: Single (Investigator)

Investigator will not know the condition assignment of individual participants unless reassessment is triggered by the stopping rule.

Allocation: Randomized

Enrollment: 343 [Actual]

3.2 Allocation to Interventional Group

Participants who completed the required tasks during the baseline period were randomized within blocks [blocked by gender (male, female, other) and smoking level (high, low; high was 20 cigarettes or greater per day)]. At the beginning of data collection, condition assignment was fully random; blocked-randomization was implemented part-way through the study on 12/01/2022.

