5.2.2 Observational Phase

The baseline period will begin after completion of Session 1, and will last for 14 days. During the baseline period, participants will complete EMA and location tracking.

- Participants will be excluded for non-compliance at the end of the baseline period if they have not responded to at least 75% of EMA prompts.
- Following the baseline period, participants will be assigned to an experimental condition.

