6.1 Sample Size and Power Determination

Our initial target was to obtain 60 complete datasets (meaning that participants finished Online Session 3, two fMRI sessions [before and after the intervention period], and also completed all 20 store visits) per intervention condition (total $N = 180$). Due to pandemic-related resource constraints and time delays, we were unable to reach this goal. We collected the maximum number of participants possible with the resources available from our grant. Prior to looking at the data, we elected to randomize more individuals into the experimental conditions than to the control condition, since less than 50% of participants typically completed all 20 store visits and provided fully complete datasets. Before we conducted any hypothesis testing, we reassessed power in consultation with our study team's biostatistician to determine which original hypotheses would be adequately powered with the available data and planned analysis.

methods. Using PANGEA, we estimated that with at least 40 complete datasets (participants who completed all 20 store visits) in each intervention condition, we could detect interaction effects (time * group) sized $d = 0.1$ with 95% power. We ultimately randomized 105 to the Non-tobacco retailer condition, 107 participants to the Tobacco retailer condition, and 70 participants to the Control condition resulting in 175 complete datasets. We scanned as many participants as we were able to obtain within constraints of the larger study. Power analysis suggests that with $N=32$ and at least 10 observations per condition in the fMRI dataset, per participant, we have $>80\%$ power to detect effects of $d = .2$ (i.e., a small effect size) within person.

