6.3.2 Analysis of Primary Outcome of Interest

Daily cigarette and craving analyses

Hypothesis 1: Reported craving will be higher for those in the Tobacco retailer condition, relative to the Control and Nontobacco retailer conditions, during the intervention phase, but not the baseline phase. To test hypothesis 1, we will use a linear mixed effects model (in R). To examine associations between study phase and craving, we will create a binary Study Phase variable indicating whether an observation for a participant occurred during the baseline (0) versus intervention (1) phase. To examine associations between condition assignment and craving, we will create two dummy coded variables indicating the condition assignment for each participant. A Control condition variable indicates whether the condition assignment is the Control condition (1) or the other two conditions (i.e., Tobacco and nontobacco retailer) (0). A Nontobacco retailer condition variable indicates whether the condition is the Nontobacco retailer condition (1) or the other two conditions (i.e., Control and Tobacco retailer conditions) (0). Thus, the Tobacco retailer condition is indicated when both the Control condition and Nontobacco retailer condition variables are equal to 0. We will test the interactions between study phase and condition assignment.

At level 1, the formal model is constructed as:

$$\text{Craving}_{it} = \beta_{0i} + \beta_{1i}\text{StudyPhase}_{it} + e_{it}$$

where β_{0i} is the intercept, indicating the average level of craving for the prototypical participant in the sample; β_{1i} indicates the difference in the level of craving between the baseline phase and intervention phase; and e_{it} are residuals that are allowed to autocorrelate.

Person-specific intercepts and associations (from the Level 1 model) are specified (at Level 2) as:

$$\begin{aligned}\beta_{0i} &= \gamma_{00} + \gamma_{01}\text{ControlCondition}_i + \gamma_{02}\text{NontobaccoRetailerCondition}_i + u_{0i} \\ \beta_{1i} &= \gamma_{10} + \gamma_{11}\text{ControlCondition}_i + \gamma_{21}\text{NontobaccoRetailerCondition}_i + u_{1i}\end{aligned}$$

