where the γ s are sample-level parameters and the u s are residual between-person differences that may be correlated with each other but are uncorrelated with e_{it} . Parameters γ_{11} and γ_{21} test the key hypotheses that craving will be higher for those in the Tobacco retailer condition, relative to the Control condition, during the intervention phase but not the baseline phase (γ_{11}) and that craving will be higher for those in the Tobacco retailer condition, relative to the Nontobacco retailer condition, during the intervention phase but not the baseline phase (γ_{21}).

Hypothesis 2: Reported cigarettes smoked will be higher for those in the Tobacco retailer condition, relative to the Control and Nontobacco retailer conditions, during the intervention phase, but not the baseline phase. To test hypothesis 2, we will use a linear mixed effects model (in R). To examine associations between study phase and cigarettes smoked, we will create a binary Study Phase variable indicating whether an observation for a participant occurred during the baseline (0) versus intervention (1) phase. To examine associations between condition assignment and cigarettes smoked, we will create two dummy coded variables indicating the condition assignment for each participant. A Control condition variable indicates whether the

condition assignment is the Control condition (1) or the other two conditions (i.e., Nontobacco retailer and Tobacco retailer conditions) (0). A Nontobacco retailer condition variable indicates whether the condition is the Nontobacco retailer condition (1) or the other two conditions (i.e., Control and Tobacco retailer conditions) (0). Thus, the Tobacco retailer condition is indicated when both the Control condition and Nontobacco retailer condition variables are equal to 0. We will test the interactions between the study phase and condition assignment.

At level 1, the formal model is constructed as:

$$Smoking_{it} = \beta_{0i} + \beta_{1i} StudyPhase_{it} + e_{it}$$

where β_{0i} is the intercept, indicating the average number of cigarettes smoked per day for the prototypical participant in the sample; β_{1i} indicates the difference in the level of craving between the baseline phase and intervention phase; and e_{it} are residuals that are allowed to autocorrelate.

Person-specific intercepts and associations (from the Level 1 model) are specified (at Level 2) as:

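### The H1 and H2 models leave out the randomisation blocking factors (gender and smoking level); if either factor predicts baseline-to-intervention change, the tests may be slightly conservative and less precise than they could be.

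*Combined protocol and SAP*

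**What the plan says.** **Allocation.** Section 3.2 states that participants were "randomized within blocks [blocked by gender (male, female, other) and smoking level (high, low; high was 20 cigarettes or greater per day"). It adds: "At the beginning of data collection, condition assignment was fully random; blocked-randomization was implemented part-way through the study on 12/01/2022". Section 5.2.2 places assignment after the two-week observational phase: "Following the baseline period, participants will be assigned to an experimental condition". Both factors could therefore be known before randomisation.

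**Analysis.** For each of craving (H1) and cigarettes smoked (H2), section 6.3.2 says "we will create two dummy coded variables indicating the condition assignment for each participant". For craving it says "We will test the interactions between study phase and condition assignment", and the cigarette paragraph repeats this almost word for word. The Level-2 equations for the intercept and for the StudyPhase slope each hold a constant, the Control dummy, the Nontobacco dummy and a person-level residual. The key parameters are gamma11 (Tobacco against Control) and gamma21 (Tobacco against Nontobacco), both in the slope equation.

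**Elsewhere.** No section names a covariate for H1 or H2. The table in section 3.3 has a heading that mentions covariates, but it lists measures and schedules, not model terms. Section 6.2 allows alternative statistics in the light of observed distributions, which does not add the blocking factors.

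**The concern.** Blocking on a factor balances it across arms, so the true sampling variance of the arm contrast falls. A model that omits the factor does not register this. It leaves the variance explained by the factor in the residual and computes the standard error as if balance had been left to chance. If the factor predicts the outcome being compared, the reported standard error is too large and the test rejects a true null less often than its nominal level.

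Here the outcome being compared is within-person change between phases. A factor matters only as far as it predicts that change. For H2 there is a plausible route: if people cut down roughly in proportion to what they smoke, heavier smokers lose more cigarettes per day. For craving, the documents give no reason to expect a relation.

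What is at stake is precision. Section 6.1 says the original target could not be reached and that recruitment went as far as the grant allowed, so further precision has to come from the analysis.

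**Working it through.** The plan gives no figure for the effect of the blocking factors, so there is none to reproduce. The power statement in section 6.1 comes without variance components and is not used here.

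**Inputs from the documents.** Randomised: 107 Tobacco, 105 Nontobacco, 70 Control, 282 in all (6.1). Complete datasets: 175 (6.1). Two-sided alpha 0.05 (6.2). Blocking began on 12/01/2022 (3.2).

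**Assumed inputs.** R² is the share of variance in observed person-level change explained by gender and smoking level, taken as 0, 5%, 10% and 20%. The number randomised under blocking is not stated; 162 of 282 is used, with a range of 80 to 200. Write f for that number divided by 282.

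**1. Which missing terms matter.** In six simulated random-slope datasets (282 people; the factor explained 11% of the variance in underlying change), the standard error of phase × Control was 0.3884 with no factor, 0.3885 with the factor on the intercept only, and 0.3762 with it on intercept and slope. Intercept terms cancel in within-person change; the StudyPhase interaction does the work. The reduction, 1 − 0.3762/0.3884 = 3.1%, is smaller than 11% would suggest because day-to-day noise dilutes the share in observed change.

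**2. Precision.** Unadjusted over adjusted standard error = 1/√(1 − R²). Equivalent loss of people = R² × N.

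| R² | SE excess | of 282 | of 175 |
|---|---|---|---|
| 0 | 0% | 0 | 0 |
| 5% | 1/√0.95 − 1 = 2.6% | 14 | 9 |
| 10% | 1/√0.90 − 1 = 5.4% | 28 | 18 |
| 20% | 1/√0.80 − 1 = 11.8% | 56 | 35 |

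Both values of N are shown because section 6.3.2 names no analysis set. The loss applies to everyone, blocked or not. Where the adjusted test would have 80% power, the unadjusted test has about 78%, 76–77% and 71–73% at the three non-zero values of R².

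**3. Type I error of the unadjusted test.** Only blocked participants contribute, so the true variance is about (1 − f·R²) times the model-based one, and type I error = 2 × [1 − Φ(1.96/√(1 − f·R²))].

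| R² | 80 blocked | 162 blocked | 200 blocked |
|---|---|---|---|
| 5% | 4.84% | 4.67% | 4.60% |
| 10% | 4.68% | 4.35% | 4.20% |
| 20% | 4.36% | 3.72% | 3.44% |

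A simulation of person-level change (6,000 runs per setting, 162 blocked) gave 4.8%, 4.5% and 3.9% unadjusted, and 5.4%, 5.1% and 5.0% adjusted. Monte Carlo error is about 0.28 points, so at R² = 5% neither test can be told apart from 5%.

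**4. Is a non-zero R² plausible for H2?** In a simulation assuming a usual level of about 14 cigarettes per day, 14 baseline and 28 intervention days, and everyone cutting by 10% to 30% of their usual level, smoking level explained 3–17% of the variance in change when taken from a screening report and 5–22% when taken from baseline EMA. Smoking level is a cut of a quantity that also enters the H2 outcome, so bias was checked: after adjustment the bias in gamma11 was at most 0.02 cigarettes per day (Monte Carlo error 0.01), with type I error 4.0–5.3%.

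**5. Cost if the factors are irrelevant (R² = 0).** The standard error of gamma11 rose from 0.153 to 0.155 SD (1.3%) in a model that also carried period terms. In a separate simulation that adjusted for the blocking strata, with half the participants blocked, it rose from 0.1539 to 0.1545 (0.4%).

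**The case against.** The strongest reply is that the loss is conditional. No passage says that gender or smoking level predicts change; R² and the number blocked are assumptions; and the H2 support rests on an across-the-board reduction that the plan does not predict. At R² = 0 the adjusted model is marginally worse, and at 5% the gain is small. All of that stands, so the conclusion has to be worded as something that may happen.

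The remedy also needs decisions that the plan does not supply. Section 3.2 does not say which measurement defined 20 cigarettes per day, and the third gender category is likely to be sparse. That stands too, but both can be settled without sight of outcomes.

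Three stronger readings are tempting and not supported:

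- *The tests are invalid.* They are not. Leaving out blocking factors cannot push type I error above nominal here; it can only lower it.
- *Omitting randomisation period also makes the tests conservative.* Period was not a blocking factor, so its omission cannot do this. It could matter only in the other direction, as bias in Tobacco against Control, and only if the allocation ratio changed and change in the outcome differed between periods.
- *The ratio did change part-way.* Section 6.1 says "Prior to looking at the data, we elected to randomize more individuals into the experimental conditions than to the control condition", without a date. The final counts fit a constant 3:3:2 ratio: 282 × 3/8 = 105.75 and 282 × 2/8 = 70.5, against 105, 107 and 70. The documents do not state a change.

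**Conclusion.** The mismatch between allocation and analysis is certain from the text. Its consequence is small and conditional. If gender or smoking level predicts baseline-to-intervention change, the tests of gamma11 and gamma21 lose some precision for all participants and may be slightly conservative through those randomised after 12/01/2022. Over assumed R² of 5% to 20%, the standard error is 2.6% to 11.8% larger than it need be and type I error lies between about 4.8% and 3.4%, depending on how many were blocked. The case is better for H2 than for H1. The planned tests remain valid; this is an inexpensive improvement that should be made.

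**What to change.** Add gender and smoking level (20 or more cigarettes per day) to both Level-2 equations of H1 and H2, so that each enters as a main effect and as an interaction with StudyPhase. The interactions are the part that matters. Fix a rule for pooling the third gender category without sight of outcomes. Use the values that were used for blocking; for people randomised before 12/01/2022, derive them by the same rule from data collected before randomisation, and state which measurement defines smoking level.

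If hypothesis testing is already done, keep the stated model as primary and report the adjusted model as a labelled sensitivity analysis.

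Cost: a few lines of SAP text, four fixed effects with gender pooled to two levels, and about a 1% larger standard error if the factors explain nothing.

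As a reporting point only, state the allocation ratio or ratios, the dates they applied, and the numbers per arm before and after 12/01/2022. A period-by-StudyPhase term is needed only if the ratio did in fact change during recruitment.
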